7.5 SECONDARY ENDPOINT(S)

7.5.1 Key secondary endpoint(s)

This section is not applicable as no key secondary endpoint has been specified in the protocol.

7.5.2 (Other) Secondary endpoint(s)

[figure not shown]
For the secondary endpoints,

- Patients achieving a decrease of at least 30% absolute change in First Morning Void urine of UACR from baseline after 14 weeks of trial treatment,
- Patients achieving a decrease of at least 15% absolute change in First Morning Void urine of UACR from baseline after 14 weeks of trial treatment.

Descriptive statistics will be provided for the number and percentage of responders in terms of UACR reduction from baseline using complete case analysis, multiple imputation, missing as non-responder, and last observation carried forward (LOCF).

- Complete case analysis uses patients with both baseline and Week 14 data available.
- Multiple imputation fills in missing values at Week 14 based on other data observed in the same patient using regression.
- Missing as non-responder imputes patients with missing Week 14 data as non-responders.
- LOCF uses the last value observed on treatment to substitute all missing values until Week 14.

The odds ratio, 95% confidence interval, and p-value will be calculated based on logistic regression of binary outcome adjusting for treatment, and stratification factors as covariates.

7.7 EXTENT OF EXPOSURE

Descriptive statistics are planned for this section of the CTR based on the TS. The date and time of each drug administration will be listed for each patient.

7.8 SAFETY ANALYSIS

All safety analyses will be performed on the TS following BI standards. No hypothesis testing is planned. Safety data will be summarised for Run-in Period and Treatment Period, respectively.

7.8.1 Adverse Events

Analyses of AEs will be descriptive in nature. All analyses of AEs will be based on the number of patients with AEs and NOT on the number of AEs.

Furthermore, for analysis of AE attributes such as duration, severity, etc. multiple AE occurrence data on the CRF, will be collapsed into AE episodes provided that all of the following applies:

- The same MedDRA lowest level term was reported for the occurrences
- The occurrences were time-overlapping or time-adjacent (time-adjacency of 2 occurrences is given if the second occurrence started on the same day or on the day after the end of the first occurrence)
- Treatment did not change between the onset of the occurrences OR treatment changed between the onset of the occurrences, but no deterioration was observed for the later occurrence

For further details on summarisation of AE data, please refer to "Analysis and presentation of adverse event data from Clinical Trials" [\(9\)](#) and "Handling of missing and incomplete AE da [\(4\)](#).

The analysis of AEs will be based on the concept of TEAEs. That means that all AEs occurring between the first drug intake until 7 days after last drug intake will be assigned to

actual treatment groups. All AEs occurring before first drug intake of empagliflozin/ placebo will be assigned to ‘screening’ and all AEs occurring after EoT + 7 days will be assigned to ‘follow-up’ (for listings only). AEs that start before first drug intake and during Run-in Period and deteriorate under treatment will also be considered as ‘treatment-emergent’. For details on the treatment definition, see [Table 6.1:1](#) in [Section 6.1](#).

If only the start date of an AE is collected (without start time), any AE occurrence on the same day as the first empagliflozin or BI 690517 administration will be assigned to the run-in or on-treatment phase, respectively. In addition, a summary of patients with down-titration due to AE will be provided.

An overall summary of AE will be presented for treated set during Run-in and on-treatment periods, respectively. This will show the number and percentage of patients with any AE, severe AEs, any investigator defined drug-related AEs, AEs of Special Interest (AESIs), AEs leading to the discontinuation of empagliflozin or BI 690517, and down-titration (dose reduction) of BI 690517, and serious AEs (SAEs).

Frequencies [N (%)] of patients with AEs during run-in period will be summarised by treatment, primary system organ class, and preferred term (using MedDRA). Separate tables will be provided for patients with SAEs, patients with AESIs, patients with any investigator defined drug-related AEs to empagliflozin, and patients with discontinuations of empagliflozin due to AEs.

Frequencies [N (%)] of patients with AEs during on-treatment period will be summarised by treatment, primary system organ class, preferred term (using MedDRA), and intensity. Separate tables will be provided for patients with SAEs, patients with AESIs, patients with fatal AEs, patients with any investigator defined drug-related AEs (with regards to empagliflozin or BI 690517), patients with down-titration (dose reduction) of BI 690517, patients with ACTH related AEs, and patients with discontinuations (of empagliflozin or BI 690517 or ACTH) due to AEs.

In addition, summary of AEs collected on special AE eCRF pages (AE - hypotension, AE - hyperkalaemia, AE - Ketoacidosis, AE - Adrenal insufficiency, and AE - Acute Kidney Injury) will be presented for both patient-based and event-based analyses.

Subgroup analysis on hypotension based on baseline BP and the lowest BP during the episode will be carried out. Criteria for significant (vs. non-significant) hypotensive episode are as follows:

- Baseline SBP ≤ 140 : decrease $\left(\frac{\text{lowest SBP during the episode} - \text{baseline SBP}}{\text{baseline SBP}} \right) \geq 30\%$;
- Baseline SBP > 140 : decrease $\left(\frac{\text{lowest SBP during the episode} - \text{baseline SBP}}{\text{baseline SBP}} \right) \geq 40\%$;
- Or, lowest SBP during the episode < 90 .
- Baseline DBP ≤ 70 : $\left(\frac{\text{lowest DBP during the episode} - \text{baseline DBP}}{\text{baseline DBP}} \right) \geq 30\%$;
- Baseline DBP > 70 : $\left(\frac{\text{lowest DBP during the episode} - \text{baseline DBP}}{\text{baseline SBP}} \right) \geq 40\%$;
- Or, lowest DBP during the episode < 50 .

- Lowest mean arterial pressure (MAP) during the episode < 70, where MAP is calculated as $MAP = \frac{SBP + 2(DBP)}{3}$

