³Visit 5 should be no more than 7 days after Visit 4. Where the patient does not meet the additional inclusion criteria 13 and 14 based on lab tests performed at Visit 4, the eGFR and potassium cannot be re-tested and the patient should permanently discontinue the study. In case of unexpected delay of Visit 5, a repeat safety sample must be taken to obtain potassium and eGFR results needed to confirm eligibility for the Treatment Period.

⁴In case a patient needs or wishes to terminate all trial treatment prematurely and if the patient agrees, the patient should undergo the procedures for End of Treatment (EoT). Please see [section 6.2.5](#) for details.

⁵Follow-up Visit 1 (FU1) must always take place at least 7 days after the EoT visit.

⁶These visits can either be performed at the Investigational site or at the patient's home. All local approvals for this must be in place and confirmed by the sponsor. Consent for home visits must also be obtained from the patient. See [section 6.2.2](#) for further details.

⁷There are various ways that Telemedicine contacts (phone call or video call) can be used during this trial:

1. Telemedicine contact to provide support for patient's urine sampling. Before the patient does their first UACR sampling at home the investigational site staff should contact the patient to ensure the patient is comfortable with the sampling process. The other timepoints marked as '(X)' are suggested times to contact the patient if they are shipping samples directly from home to ensure they understand the instructions given to them. The site may, at their discretion, offer support with further home sampling according to the individual needs of a patient.
2. Visit 3 must be performed as telemedicine contact for all patients, unless they prefer to come to the trial site instead.
3. Phone/ video calls may also take place at any other time if needed to support the patient.

⁸Informed consent must be obtained before the first screening assessment. It can be obtained on the day of the screening visit or within 4 weeks prior to the first screening assessment. The consent discussion should include showing the patient the home sampling kits and explaining this procedure.

⁹All ECGs will be done prior to the daily dose and evaluated by the investigator or a designee. See [section 5.2.4](#).

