¹⁰ACTH Challenge test is required for all patients at screening, and for all patients whose morning serum cortisol level at EoT (or at the time of premature discontinuation of BI 690517 / placebo) is < 18 µg/dL (496.6 nmol/L). After the start of BI 690517 / placebo treatment at Visit 5, if morning serum cortisol level is ≥ 3 µg/dL (82.8 nmol/L) and < 11 µg/dL (303.5 nmol/L) and the patient shows suggestive signs or symptoms of adrenal insufficiency, an ACTH Challenge test should be performed as soon as possible. Serum cortisol basal sample must be performed before ACTH- injection (0.25 mg). Injection time must be recorded and has to be done within 4 hours of the patient's usual waking time. Post-dose samples for serum cortisol must be taken 30 (± 5) minutes after the injection, to ensure patients have normal adrenal function. The time for the post ACTH-injection blood samples must be recorded in the patient's medical record. See [section 5.2.5.1](#).

¹¹Patients do not need to be fasted for the blood sampling for the safety laboratory. See [section 5.2.3](#).

¹²eGFR at clinic visits will be determined from serum creatinine analysed by the central laboratory. To confirm eligibility, the eGFR at screening will be used.

¹³

¹⁴Lab samples for serum cortisol must be collected within 4 hours of the patient's usual waking time.

¹⁵Post-dose serum cortisol should be taken 1 hour (\pm 10 minutes) after drug administration.

¹⁶See [Flow Chart](#) for samples and timings. For further instructions see [section 6.1](#).

¹⁷The pharmacogenomics samples may be collected at Visit 5 or anytime afterwards.

¹⁸Optional biobanking samples will only be collected if the patient has signed the biobanking informed consent separate from the main consent for the trial. See [section 5.5](#).

¹⁹A pregnancy test is required for all women of child-bearing potential. This will be a serum pregnancy at Screening (Visit 1). Thereafter a urine pregnancy test will be performed. A home pregnancy test may be used at the Visit 3 timepoint. If urine pregnancy test is not acceptable to local authorities, a blood test can be done at a local laboratory. More frequent pregnancy testing should be done if required by local regulation and/or authority or per investigator judgment.

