5.2.5 Other safety parameters

5.2.5.1 ACTH challenge test

An ACTH challenge test will be performed for all patients at screening to ensure patients have normal adrenal function.

An ACTH Challenge test will also be performed during the study:

- between the start of BI 690517 / matching placebo treatment at Visit 5 and end of BI 690517 / placebo treatment, if the morning serum cortisol level is $\geq 3 \mu\text{g/dL}$ (82.8

nmol/L) and $< 11 \mu\text{g/dL}$ (303.5 nmol/L) and the patient shows suggestive signs or symptoms of adrenal insufficiency (see [section 4.2.1.3](#)), and

- after the end of BI 690517 / matching placebo treatment (either at EoT, or when BI 690517 / placebo is prematurely permanently discontinued), if the morning serum cortisol level is $< 18 \mu\text{g/dL}$ (496.6 nmol/L).

In these cases, the ACTH Challenge test should be performed as soon as possible.

A serum cortisol basal sample must be taken before the ACTH injection (iv or im 0.25 mg Synacthen®; an equivalent product may be used if Synacthen® is not authorised locally or provided by the sponsor). The injection time must be recorded. Serum cortisol will be determined 30 (± 5) minutes after the injection. The time for the post-ACTH injection blood samples must be recorded. The ACTH Challenge test can be performed by a local or central laboratory.

Patients will be monitored closely for at least 30 minutes after the injection.

Alternative conduct of the ACTH test is allowed only if it is in accordance with the local practice of diagnosis of adrenal insufficiency. If adrenal insufficiency is diagnosed with an alternative conduct of ACTH test, the details of the ACTH test should be documented in the AESI report to the sponsor.

In this trial, the Synacthen® (or equivalent product) for the ACTH challenge test is considered as auxiliary medicinal product (AxMP). In some countries, however, (for example, Germany) it is considered as investigational medicinal product (IMP) for regulatory reasons. For a more detailed description of Synacthen® please refer to the current Summary of Product Characteristics (SmPC).

5.2.5.2 eGFR

eGFR will be analysed and calculated by the central laboratory at the timepoints indicated in the [Flow Chart](#).

eGFR will be calculated by using the CKD-EPI formula (see [section 10.2](#))

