5.2.6.1.4 Adverse events of special interest

The term adverse events of special interest (AESI) relates to any specific AE that has been identified at the project level as being of particular concern for prospective safety monitoring and safety assessment within this trial, e.g. the potential for AEs based on knowledge from other compounds in the same class. AESIs need to be reported to the sponsor’s Pharmacovigilance Department within the same timeframe that applies to SAEs, please see [section 5.2.6.2.2](#).

The following are considered as AESIs:

- 1) Potential Severe DILI
- 2) Events leading to lower limb amputation (LLA)
- 3) Ketoacidosis
- 4) Cushing’s syndrome
- 5) Adrenal insufficiency

Potential Severe DILI

A potential severe Drug Induced Liver Injury (DILI) that requires follow-up is defined by the following alterations of hepatic laboratory parameters:

- An elevation of AST (Aspartate Aminotransferase) and / or ALT (Alanine Aminotransferase) ≥ 3 -fold ULN combined with an elevation of total bilirubin ≥ 2 -fold ULN measured in the same blood sample, or in samples drawn within 30 days of each other, or
- ALT and / or AST elevations ≥ 10 -fold ULN.

These lab findings constitute a hepatic injury alert and the patients showing these lab abnormalities after the start of study treatment need to be followed up according to the “DILI checklist” provided in the eDC system.

In case of clinical symptoms of hepatic injury (icterus, unexplained encephalopathy, unexplained coagulopathy, right upper quadrant abdominal pain, etc.) without lab results (ALT, AST, total bilirubin) available, the investigator should make sure these parameters are analysed, if necessary, in an unscheduled blood test. Should the results meet the criteria of hepatic injury alert, the procedures described in the DILI checklist should be followed.

Events leading to lower limb amputation (LLA)

Any event leading to a lower limb procedure of amputation, auto-amputation or disarticulation as defined below is considered as an AESI.

Amputation is a resection of a limb through a bone. Disarticulation is a resection of a limb through a joint. Auto-amputation is a spontaneous separation of non-viable portion of the lower limb.

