Run-in	Placebo, Empagliflozin, respectively	Date / time of first administration of empagliflozin / placebo	For patients discontinue in Run-in Period, 12:00 a.m on the day after last administration of empagliflozin / placebo + REP (7 days),

			For patients continue in Treatment Period, 12:00 a.m on the day after last administration of empagliflozin / placebo + REP (7 days) or first administration of BI 690517 / placebo, whichever occurs first
On-treatment	Placebo, BI 690517, Plus Empagliflozin or matching placebo, respectively	Date / time of first administration of BI 690517 / placebo	12:00 a.m on the day after last administration of BI 690517 / placebo + REP (7 days) Or 12:00 a.m on the day after patient's trial termination date,
Follow-up ¹	F/U Placebo, F/U BI 690517, plus Empagliflozin or matching placebo, respectively	12:00 a.m on the day after last administration of BI 690517 / placebo + REP (7 days)	12:00 a.m on the day after patient's trial termination date

¹ Follow-up phase might not exist, e.g. if the patient's trial termination date is within 7 days after last administration of study drug

In the case that the patient is permanently discontinued BI 690517, but is continuing on Empagliflozin during Treatment Period, the occurrence of AEs between REP of BI 690517 and REP of Empagliflozin will be provided in the listing. For treatment interruptions, the occurrence of AEs between the start of interruption and re- start of treatment will be assigned to actual treatment received. These cases will be flagged in the safety listings as occurring during the off-treatment period. AEs will be displayed by dose group and will be provided in the CTR.

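### Adrenal insufficiency found by the end-of-treatment ACTH test is left out of the on-treatment AESI table if it is dated 8 or more days after the last BI 690517/placebo dose

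*SAP*

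**What the plan says.** **Protocol.** Flow Chart footnote 10 requires an ACTH challenge test "for all patients whose morning serum cortisol level at EoT (or at the time of premature discontinuation of BI 690517 / placebo) is" below 18 µg/dL. Symptoms are not needed. Section 5.2.5.1 places this test "after the end of BI 690517 / matching placebo treatment (either at EoT, or when BI 690517 / placebo is prematurely permanently discontinued"). On timing it says only: "In these cases, the ACTH Challenge test should be performed as soon as possible". The trigger during treatment is narrower: cortisol of at least 3 and below 11 µg/dL, and in addition "the patient shows suggestive signs or symptoms of adrenal insufficiency, an ACTH Challenge test should be performed as soon as possible". Section 3.3.4.1 counts a 30-minute stimulated cortisol below 18 µg/dL as adrenal insufficiency, and section 5.2.6.1.4 lists it as an AESI: "5) Adrenal insufficiency".

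**SAP.** Section 7.8.1 builds its treatment-period AE tables, including the AESI table, on the on-treatment period. Table 6.1:1 in section 6.1 ends that period (exclusive) at "12:00 a.m on the day after last administration of BI 690517 / placebo + REP (7 days"). Section 7.8.1 adds that "all AEs occurring after EoT + 7 days will be assigned to" follow-up, for listings only. Section 6.1 also sends to a listing any AE that falls between the end of the BI 690517 residual effect period (REP) and that of empagliflozin, in patients who stop the first drug and continue the second.

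Separately, section 7.8.1 plans patient-based and event-based summaries of the special AE eCRF pages, one of which is adrenal insufficiency. No period is given for them.

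**The concern.** Of the ACTH tests after screening, the one at the end of treatment has the widest trigger, because it needs no symptoms and uses the higher cortisol limit. It is also the only one that by design follows the last dose. Its result can therefore arrive after the date on which the SAP stops tabulating AESIs.

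Whether a case appears in the by-arm AESI table then depends on two things unrelated to the drug: how soon the site could arrange the test, and which onset date it entered. Neither document says whether a case found by the test is dated to the low cortisol, to the first symptom or to the test itself. Amendment 1 added the serum cortisol samples and the on-study ACTH tests to detect adrenal insufficiency, so the by-arm display of what they find should not rest on those choices.

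**Working it through.** No power or sample-size figure is involved. The check is date arithmetic on the Flow Chart and SAP Table 6.1:1.

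**Inputs**
- EoT is Day 99, and BI 690517/placebo is given at that visit (Flow Chart).
- FUp1 is Day 106 with a window of +3 days, and FUp2 is Day 127 (Flow Chart). Footnote 5 says that FUp1 "must always take place at least 7 days after the EoT visit".
- The REP is 7 days (SAP 6.1).
- The on-treatment phase ends at 00:00 on the day after last BI 690517/placebo dose + 7 days (SAP Table 6.1:1).

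**Step 1: completer**
- Last dose + REP = 99 + 7 = Day 106.
- The phase ends at 00:00 on Day 106 + 1 = Day 107.
- An AESI dated 0 to 7 days after the last dose (Days 99 to 106) is in the AESI table. One dated 8 or more days after it (Day 107 onward) is in the listing only.
- From Day 107 to nominal FUp2 there are 127 − 107 + 1 = 21 listing-only days.

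**Step 2: what decides the side of the line**
- The test date has no upper limit in days.
- The SAP allocates AEs by when they occur, and there is no onset rule for a case found by a test.
- A case stays in the table if the test falls within 7 days of the last dose, or if onset is dated to the EoT cortisol. It leaves the table only if the recorded onset is 8 or more days after the last dose.

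**Step 3: patient who stops BI 690517 early and continues empagliflozin**

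The SAP words the cut-off in three ways: last drug intake + 7 days (7.8.1), EoT + 7 days (7.8.1), and last BI 690517/placebo dose + 7 days (Table 6.1:1). They agree for a completer. As an illustration, take a last BI 690517 dose on Day 43 and empagliflozin to EoT on Day 99:
- Table 6.1:1: 43 + 7 = Day 50.
- EoT + 7: 99 + 7 = Day 106.
- Last drug intake + 7: Day 50 or Day 106, depending on which drug is meant.
- Gap: 106 − 50 = 56 days.

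SAP 7.8.2 and 7.8.3 redefine EoT for such patients, but only for laboratory data and vital signs. Section 7.8.1 has no such rule for AEs.

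**Step 4: other planned outputs**
- The adrenal insufficiency eCRF-page summary could show a late case. Its period is not stated, and the listings-only sentence in the same section could be read as limiting it.
- Laboratory displays use central-laboratory data unless otherwise specified (SAP 7.8.2), whereas the ACTH test may be run locally (Protocol 5.2.5.1). The SAP text available shows no table of ACTH test results.
- After FUp1 the protocol still collects AESIs, but only drug-related ones (5.2.6.2.1).

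**The case against.** The strongest defence has four parts. First, the cut-off follows the 7-day REP rule in Protocol 7.2.6, a conventional way to define treatment-emergent events. Second, the margin is reasonable: a completer has seven days after the last dose for a test that is to be done promptly, local laboratories are allowed, and Protocol 6.1 permits unscheduled safety visits. Third, onset is not the same as test date, and a case confirmed because the EoT cortisol was low can properly be dated to EoT or before. Fourth, the adrenal insufficiency page has its own summary, and serum cortisol is measured at every visit from Visit 5 through follow-up.

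Much of this stands. The REP convention should remain for the AESI table, and many cases may well fall inside it. What remains is that nothing guarantees this. No maximum number of days is set, no onset rule is given, and the period of the separate summary is open.

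Three stronger readings are tempting and not supported:
- **The test waits for FUp1, so most of that visit's window lies past the cut-off.** Days 107 to 109 do lie past it, but the Flow Chart marks the ACTH test at screening, Visits 5 to 9 and EoT, not at FUp1, and nothing tells sites to wait.
- **The test has no timing rule at all.** It has one; what is missing is a limit in days.
- **Late cases are tabulated nowhere.** The eCRF-page summary may include them; the SAP does not say.

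**Conclusion.** The gap is real but conditional. An adrenal insufficiency AESI that this test finds and that is dated 8 or more days after the last BI 690517/placebo dose will be missing from the on-treatment AESI table. For a completer that means Day 107 or later. This rests on the last dose being taken at EoT on Day 99 and on the recorded onset date being the date used for allocation. For patients who stop BI 690517 early and continue empagliflozin, the cut-off is also ambiguous, by 56 days in the illustration.

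How many cases are affected cannot be computed. The documents give no laboratory turnaround, recall time or expected rate of adrenal insufficiency. A reader might infer that the tabulated rate and any dose trend will be understated. The documents do not support that as a flat statement, because it would be true only if some cases were dated late. If the share dated late were the same in every arm, absolute differences would shrink while ratios between arms would hold.

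This is a low-cost SAP clarification for a safety event of declared interest. It does not touch the efficacy analyses.

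**What to change.** In SAP 6.1 and 7.8.1:

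1. Keep the on-treatment AESI table and use one cut-off throughout: last BI 690517/placebo dose + 7 days.
2. State that the adrenal insufficiency eCRF-page summary is tabulated by randomised arm through end of trial, with events after the REP shown separately. A footnote should say that only drug-related AESIs are collected after FUp1.
3. State which onset date applies to a case found by the ACTH test.
4. Add a by-arm count of patients who required the end-of-treatment ACTH test, were tested, and had stimulated cortisol below 18 µg/dL, whatever the test date.

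A supplementary display is preferable to reassigning late events to the on-treatment phase, which would override the REP convention for a single AE term. None of this changes when or how patients are tested.

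The cost is a few sentences and one small table. If locally run ACTH results are not already in the clinical database, they would have to be added. The downside is that the extra table may include a few events that arose off drug, in any arm; showing post-REP events separately lets the reader judge them.

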3.3.2 Inclusion criteria

1. Signed and dated written informed consent in accordance with ICH-GCP and local legislation prior to admission to the trial.

2. Male or female patients of legal adult age (according to local legislation) and aged ≥ 18 years at time of consent.
3. eGFR (Chronic Kidney Disease Epidemiology Collaboration [CKD-EPI] formula) ≥ 30 and < 90 mL/min/1.73 m² at Visit 1 by central laboratory analysis.
4. UACR ≥ 200 and $< 5,000$ mg/g in spot urine (midstream urine sample) by central laboratory analysis at Visit 1.¹
5. If the patient is taking any of the following medications they should be on a stable dose for at least 4 weeks prior to visit 1 and until first randomisation prior to run-in with no planned change of the therapy during the trial: anti-hypertensives, NSAIDs, endothelin receptor antagonists, low dose systemic steroids (e.g. prednisolone ≤ 10 mg or equivalent).
6. Treatment with a clinically appropriate, stable dose of either ACEi or ARB (but not both together), for ≥ 4 weeks prior to visit 1 and until first randomisation with no planned change of the therapy during the trial.
7. In the Investigator's opinion, any kind of diagnosed chronic kidney disease⁵. Patients with diabetic kidney disease must have type 2 diabetes mellitus and their treatment (including GLP1 receptor agonist) should be unchanged or changes deemed minor (according to investigator's judgement) within 4 weeks prior to Visit 1 and until first randomisation.
8. Glycated Haemoglobin (HbA1c) $< 10.0\%$ at Visit 1 measured by the central laboratory.
9. Serum potassium ≤ 4.8 mmol/L at Visit 1 measured by the central laboratory. (For further details, see [section 4.2.1.1](#))
10. Seated SBP ≥ 110 and ≤ 160 mmHg and DBP ≥ 65 and ≤ 110 mmHg at Visit 1 (mean values from three BP measurements) and optimised anti-hypertensive treatment according to local standard of care and investigator's judgement.
11. Body Mass Index (BMI) ≥ 18.5 and < 50 kg/m² at Visit 1.
12. Women of child-bearing potential² (WOCBP) must be ready and able to use highly effective methods of birth control according to [section 4.2.2.3](#). Such methods should be used throughout the trial. Men must be vasectomised or willing and able to use a condom if their partner is a WOCBP.

Additional inclusion criteria to be assessed before second randomisation (start of Treatment Period):

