7.8.3 Vital signs

The analyses of vital signs (blood pressure and pulse rate) will be described by descriptive statistics and figures of difference in vital signs from baseline (see [Section 6.7](#)) to the end of study. Vital signs at EoT visit are defined as EoT values. In the case that the patient is permanently discontinued for BI 690517, but is continuing on empagliflozin during Treatment Period, EoT for analysis of vital signs will be defined as the nearest scheduled visit on treatment of BI 690517.

Marked changes of seated systolic blood pressure (SBP), diastolic blood pressure (DBP), pulse rate (PR) will be summarised by the number and the percentage of patients at each visit by treatment according to the definition below:

- 1) Marked Increase: SBP > 150 mmHg and an increase of ≥ 25 mmHg above baseline
Marked Decrease: SBP < 100 mmHg and a decrease of > 10 mmHg below baseline
- 2) Marked Increase: DBP > 90 mmHg and an increase of > 10 mmHg above baseline
Marked Decrease: DBP < 60 mmHg and a decrease of > 10 mmHg below baseline
- 3) Marked Increase: PR > 100 bpm and an increase of > 10 bpm above baseline
Marked Decrease: PR < 60 bpm and a decrease of > 10 bpm below baseline.

Clinically relevant findings in vital signs will be reported as baseline conditions (at screening) or as AEs (during the trial) if judged clinically relevant by the investigator, and will be analysed as such.

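### SAP 7.8.1: for baseline DBP > 70 the hypotension criterion divides the diastolic fall by baseline SBP, so some diastolic falls of 40% or more are labelled non-significant

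*SAP*

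**What the plan says.** SAP 7.8.1 plans that "Subgroup analysis on hypotension based on baseline BP and the lowest BP during the episode will be carried out". It then gives a list under "Criteria for significant (vs. non-significant) hypotensive episode are as follows". In substance:

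| Baseline | Change divided by | Direction stated | Threshold |
|---|---|---|---|
| SBP ≤ 140 | baseline SBP | yes | 30% |
| SBP > 140 | baseline SBP | yes | 40% |
| DBP ≤ 70 | baseline DBP | no | 30% |
| DBP > 70 | **baseline SBP** | no | 40% |

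All four numerators are lowest minus baseline. In the formula text, the join of numerator and denominator reads "baseline DBP}}{\text{baseline DBP" for DBP ≤ 70 and "baseline DBP}}{\text{baseline SBP" for DBP > 70. Three absolute criteria are added: lowest SBP < 90, lowest DBP < 50, and lowest mean arterial pressure (MAP) < 70, where MAP = (SBP + 2 × DBP) / 3. Neither document restates or corrects the rule elsewhere.

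**The concern.** A diastolic change expressed as a fraction of systolic pressure is not a percentage fall in either pressure. The other three lines, with their paired 30% and 40% thresholds, point to a slip and not a choice. Because SBP exceeds DBP, the wrong denominator shrinks the computed fall and makes the criterion much harder to meet.

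The sign is a second, smaller defect. Lowest minus baseline is negative for a fall. The systolic lines call the quantity a decrease, so there the sign is only notation. The diastolic lines do not, so taken literally no diastolic fall can reach +30% or +40%.

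The label that separates significant from non-significant episodes is at stake. Hypotensive events are among those for which Protocol 5.2.6.2.4 collects extra data. A programmer must either code the formula as it stands or depart from the SAP without a record.

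**Working it through.** **Inputs.** The criteria come from SAP 7.8.1. Illustrative baselines lie within the entry limits of Protocol 3.3.2: "Seated SBP ≥ 110 and ≤ 160 mmHg and DBP ≥ 65 and ≤ 110 mmHg at Visit 1". The plan gives no figure of its own to reproduce.

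**Assumptions.** All criteria are joined by OR, although the SAP does not say how the SBP, DBP and MAP blocks combine; OR labels the most episodes significant and so favours the SAP. The lowest SBP and lowest DBP come from the same reading. Except in step 1, the diastolic lines are read as decreases.

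**Step 1: the sign alone.** For DBP ≤ 70, a 30% fall gives at most 0.7 × 70 = 49, already caught by lowest DBP < 50. The missing direction therefore changes no label in that line. For DBP > 70, read literally, the line can never be met by a fall.

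**Step 2: what the DBP > 70 line demands.** With the SBP denominator, the lowest DBP must be at or below DBP − 0.4 × SBP. With the DBP denominator, it must be at or below 0.6 × DBP.

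| Baseline | SBP denominator | DBP denominator |
|---|---|---|
| 140/90 | 90 − 56 = 34 | 54 |
| 150/95 | 95 − 60 = 35 | 57 |
| 160/100 | 100 − 64 = 36 | 60 |

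In each of these cases the lowest DBP < 50 criterion applies long before the SBP-denominator line does.

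**Step 3: where a label can change.** A 40% fall must leave DBP at 50 or above, so 0.6 × DBP ≥ 50. The smallest whole-number baseline is 84 (0.6 × 84 = 50.4; 0.6 × 83 = 49.8). From 120/80 nothing is lost, since 0.6 × 80 = 48.

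**Step 4: applying the other criteria.** Set the lowest DBP to the whole number at or just below 0.6 × baseline. The table gives the smallest lowest SBP at which SBP < 90, the relative SBP criterion and MAP < 70 are all unmet, so the episode is lost.

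| Baseline | Lowest DBP | Lost if lowest SBP is at least | SBP fall at that limit |
|---|---|---|---|
| 130/85 | 51 | 108 | 22/130 = 16.9% |
| 140/85 | 51 | 108 | 32/140 = 22.9% |
| 140/90 | 54 | 102 | 38/140 = 27.1% |
| 150/95 | 57 | 96 | 54/150 = 36.0% |
| 160/100 | 60 | 97 | 63/160 = 39.4% |

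**Step 5: two worked episodes.**

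- 140/90 to 104/54: diastolic fall 36/90 = 40.0%, computed by the SAP as 36/140 = 25.7%. The SBP fall is also 36/140 = 25.7% (threshold 30%), and MAP = (104 + 108)/3 = 70.7. Non-significant as written; significant with the DBP denominator.
- 160/110 to 110/60: diastolic fall 50/110 = 45.5%, computed as 50/160 = 31.3%. The SBP fall is 31.3% (threshold 40%), and MAP = (110 + 120)/3 = 76.7. The label changes in the same way.

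**Step 6: how often the line can act at all.** Take whole-number baselines with SBP 110–160, DBP 71–110 and pulse pressure above 20, which gives 1809 pairs. The SBP-denominator line can add to lowest DBP < 50 (DBP − 0.4 × SBP ≥ 50) in 140 pairs, all with DBP ≥ 98 and pulse pressure 21–40. The DBP-denominator line can add (0.6 × DBP ≥ 50) in 1146 pairs. These are grid cells, not patients, and the comparison is with the DBP < 50 criterion only.

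**The case against.** The strongest reply is that little depends on this. The SAP says "Analyses of AEs will be descriptive in nature", no hypothesis is tested on safety data, and every hypotension event from the special form is summarised whatever its label. No endpoint, analysis set or dosing decision in the documents uses the split. SAP 7.8.3 also tabulates "Marked Decrease: DBP < 60 mmHg and a decrease of > 10 mmHg below baseline". All of this stands and limits the effect. The separate table is only a partial safeguard: it is produced by visit, an episode's lowest reading need not fall on a visit, and 160/110 to 110/60 meets neither its DBP < 60 nor its SBP < 100 condition.

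The defect could also be a misread letter in a formula taken from PDF. That cannot be excluded, so the page must be checked. The other three fractions were read coherently, which makes a misreading less likely.

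The sign point is weak alone. The rule concerns hypotension and uses the lowest pressure, so most readers would infer the direction. It is a wording defect; the denominator causes the wrong labels.

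Finally, the grid uses Visit 1 entry limits, whereas SAP 6.7 takes baseline as the last observation before first intake. The counts of 140 and 1146 depend on those limits and on ignoring the SBP and MAP criteria. The floor of 84, the step 4 limits and the worked episodes do not.

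**Conclusion.** The concern holds. As the SAP reads, the DBP > 70 criterion has the wrong denominator and gives wrong labels even with the direction repaired and all criteria joined by OR. A stricter combination would not rescue it. Lost episodes have baseline DBP of at least 84, a lowest DBP from 50 to 0.6 × baseline, and no SBP or MAP criterion met. The SBP criteria, lowest DBP < 50 and MAP < 70 are unaffected, as are the primary endpoint, alpha and power. The share of real episodes mislabelled cannot be derived from the documents. The conclusion rests on the formula having been read correctly from the PDF, so confidence is medium until the page is checked. It is worth correcting because the rule is explicit and the repair is simple.

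**What to change.** Write all four relative criteria as (baseline − lowest) / baseline of the same pressure, keeping the sponsor's 30% and 40% thresholds and the cut-points at 140 and 70. State how the SBP, DBP and MAP blocks are joined. First check the denominator of the DBP > 70 line against the original SAP page, then confirm that the analysis program matches the corrected text. The cost is SAP wording, plus one line of code if the formula was programmed as written; no new data are needed.
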